## 1 Introduction

### 1.1 Background

Chronic Spontaneous Urticaria (CSU) is defined as the spontaneous occurrence of itchy wheals (hives), angioedema or both lasting for at least 6 weeks (Zuberbier et al 2018). The classic description of urticaria is a wheal and flare with a pale elevated lesion and surrounding erythema, ranging in size from a few millimeters to a few centimeters across, usually occurring in groups and often coalescing to form large confluent lesions. CSU can be debilitating and is associated with intense itching and has a major impact on patient's well-being, suggested to be comparable to that of severe coronary artery disease (Greaves 2003). The symptoms of urticaria and urticarial-associated angioedema adversely affect daily activities and sleep (O'Donnell et al 1997). The burden of CSU on health-related quality of life (HRQoL) and work productivity is substantial (Maurer et al 2017).

Second generation H1-antihistamines are recommended as first line treatment for subjects with CSU but less than 40% of these subjects respond adequately (Guillén-Aguinaga et al 2016). While uptitration of second generation antihistamines is recommended by most CSU treatment guidelines as second line therapy (Zuberbier et al 2018), the efficacy of uptitrated H1-antihistamines in CSU, beyond the approved label dose, has not been studied in larger clinical studies. Omalizumab is a highly effective third line therapy for CSU subjects. However, less than 50% of subjects treated with omalizumab reach a complete control of signs and symptoms of CSU (Kaplan et al 2016). Therefore, there is a high medical need for new treatment options for CSU subjects.

Bruton's tyrosine kinase (BTK) is a cytoplasmic tyrosine kinase and member of the TEC kinase family. BTK is expressed in selected cells of the adaptive and innate immune system including B cells, macrophages, mast cells/basophils and thrombocytes. BTK is indispensable for signaling through the Fc epsilon receptor (FcεR1 for IgE) and the activating Fc gamma receptors (FcγR for IgG), as well as the B cell antigen receptor (BCR) and BTK inhibitors (BTKi) like ibrutinib are approved for the treatment of B cell malignancies (Hendriks et al 2014). Recently, it has been demonstrated that inhibition of BTK leads to inhibition of mast cell and basophil activation/degranulation in vitro and to reduced wheal sizes in skin prick tests with patients suffering from IgE-mediated allergies (Smiljkovic et al 2017; Regan et al 2017; Dispenza et al 2018). Thus, BTK inhibition is a promising therapeutic concept for the treatment of chronic urticaria.

LOU064 is a low molecular weight compound for oral administration that covalently binds and inhibits BTK with high selectivity. It has been shown to effectively inhibit basophil activation in healthy volunteers and CSU patients as measured by the inhibition of CD63 up-regulation. Additionally, LOU064 reduced wheal sizes in skin prick tests. The pre-clinical and clinical safety profile of LOU064 is favorable (for detailed information please refer to the Investigator's Brochure (IB)). Thus, LOU064 may offer a novel therapeutic option for treating CSU.

[figure not shown]
### 1.2 Purpose

The purpose of this study is to evaluate long-term safety and tolerability as well as efficacy outcome of LOU064 in patients who roll-over from CLOU064A2201.

## 2 Objectives and endpoints

Table 2-1 Objectives and related endpoints

Objective(s)	Endpoint(s)
Primary objective(s)	Endpoint(s) for primary objective(s)

To assess the long-term safety and tolerability of LOU064 in patients with CSU who have participated in CLOU064A2201.

	

Safety endpoints will include but not be limited to: occurrence of treatment emergent (serious and non-serious) adverse events during the extension study

Secondary objective(s)	Endpoint(s) for secondary objective(s)

To evaluate the efficacy of LOU064 when given without H1-antihistamines in patients with CSU who have participated in CLOU064A2201 with respect to change from baseline in UAS7, achieving controlled disease (defined by a UAS7≤6), and achieving complete response (defined by a UAS7=0) at Week 4 of treatment

To evaluate the long-term efficacy of LOU064 in patients with CSU who have participated in CLOU064A2201 with respect to maintaining or achieving controlled disease (defined by a UAS7≤6) over time

To evaluate the long-term efficacy of LOU064 in patients with CSU who have participated in CLOU064A2201 with respect to change from baseline in UAS7 over time

	

Change from baseline in UAS7 at Week 4

UAS7≤6 response at Week 4

UAS7=0 response at Week 4

UAS7≤ 6 response over time

Change from baseline in UAS7 over time

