### 3 Study design

[figure not shown]
This study is an open-label, single arm, multicenter, long-term safety and tolerability extension study for CSU patients rolling-over from CLOU064A2201. It consists of three periods ([Figure 3-1](#)):

- ***Observational period:*** Subjects rolling over from CLOU064A2201 with  $UAS7 < 16$  after the follow-up period at Week 16 will be further followed up without receiving LOU064 for up to 12 weeks. After relapse ( $UAS7 \geq 16$  at least once), the observational period can be terminated immediately at any time during these 12 weeks and subjects may enter the treatment period. Continuation of background therapy with an H1-antihistamine is at the discretion of the investigator; however, background therapy should only be interrupted in subjects with controlled CSU (e.g.  $UAS7 \leq 6$ ). Subjects who have never relapsed within 12 weeks will discontinue the study after the observational period.
- ***Treatment period:*** Subjects will be treated with 100 mg LOU064 bid for 52 weeks. Until Week 4 of treatment, no background medication with H1-antihistamines is permitted. After Week 4, subjects may start a background therapy with H1-antihistamines if deemed necessary by the investigator.
- ***Follow-up period:*** Treatment-free follow-up period following the treatment period. The minimum duration of treatment-free follow-up is 4 weeks for all subjects who stop treatment with LOU064 (either after completing the treatment period or after an early discontinuation of study treatment). Subjects who have a  $UAS7 \leq 6$  at Week 52 of the treatment period will extend their follow-up period until relapse ( $UAS7 \geq 16$ ) for up to a total of 16 weeks.

Rescue therapy to treat unbearable symptoms of urticaria on a day-to-day basis with an H1-antihistamine will be allowed throughout the study. A post-trial access program (which may be another extension study or a managed access program) for subjects who complete this study is under consideration.

**Figure 3-1** Study design

 Only when UAS7<16 at Week 16 of CLOU064A2201: Treatment-free observational period for up to 12 weeks. After relapse (UAS7 $\geq$ 16 at least once), subjects may immediately initiate treatment period. Subjects who have never relapsed within 12 weeks will discontinue the study after the observational period.

[figure not shown]

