#### 4.1.1 Rationale for choice of background therapy

Following therapeutic principles for CSU as suggested by current treatment guidelines (Zuberbier et al 2018), the core study assessed efficacy and safety of different doses of LOU064 when given together with H1-antihistamines. The mechanism of action suggests, that the addition of H1-antihistamines is not mandatory to achieve the full therapeutic potential of LOU064. Therefore, the concomitant administration of a background H1-antihistamine is at the

discretion of the investigator in this extension study.

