## **6.2 Other treatment(s)**

### **6.2.1 Concomitant therapy**

In contrast to the core study CLOU064A2201, LOU064 may be given with or without background medication, as deemed appropriate by the investigator. However, all subjects must start the treatment period (day 1 until Week 4) with LOU064 as a monotherapy without concomitant administration of H1-antihistamines. After Week 4, subjects may start a background therapy with H1-antihistamines at a locally approved licensed dose and posology if deemed necessary by the investigator.

The investigator should instruct the subject to notify the study site about any new medications (including medications that are not related to the treatment of CSU) he/she takes after the subject was enrolled into the study, ideally before initiating a new treatment. All medications, procedures and significant non-drug therapies (including physical therapy and blood transfusions) administered after the subject was enrolled into the study must be recorded on the respective eCRF pages.

Each concomitant drug must be individually assessed against all exclusion criteria/prohibited medications (see [Table 6-2](#)). If in doubt the investigator should contact the Novartis medical advisor before enrolling a subject or allowing a new medication to be started. If the subject is already enrolled, Novartis should be contacted immediately to determine if the subject should continue participation in the study.

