**Table 6-2 Prohibited medication**

Medication	Prohibition period
Biologics for treatment of CSU (including omalizumab and ligelizumab)	4 months prior to enrollment until end of study
Routine (daily or every other day during 5 or more consecutive days) doses of systemic corticosteroids	30 days prior to enrollment until end of study
Leukotriene antagonists (including montelukast and zafirlukast)	From enrollment until end of study
H2-antihistamines	From enrollment until end of study
First generation antihistamines	From enrollment until end of study
Second generation antihistamines other than the defined background medication and rescue medication	From enrollment until end of study
Other immunosuppressive medication with or without known effect on CSU including but not limited to hydroxychloroquine, methotrexate, cyclosporine A, cyclophosphamide, tacrolimus and mycophenolate mofetil	30 days or 5 half-lives (whichever is longer) prior to enrollment until end of study
Intravenous (i.v.) immunoglobulins or plasmapheresis	30 days prior to enrollment until end of study
Regular (daily or every other day) doxepin (oral)	14 days prior to enrollment until end of study
Live attenuated vaccine	6 weeks prior to enrollment until end of study
Moderate and strong inhibitors of CYP3A4 (see Table 16-5), including grapefruit juice	From enrollment until end of study
Moderate and strong inducers of CYP3A4 (see Table 16-6)	From enrollment until end of study
Any drug known to prolong QTc interval (see https://crediblemeds.org for guidance)	5 half-lives or until pharmacodynamic effect has disappeared prior to enrollment (whichever is longer) until end of study
Anti-platelet or anticoagulant medication (for example, warfarin, or clopidogrel or Novel Oral Anti-Coagulant - NOAC) other than acetylsalicylic acid (up to 100 mg/d)	From enrollment until end of study

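### The Week 4 objective is efficacy without H1-antihistamines, but rescue H1-antihistamine is allowed in Weeks 1-4 and the visible analyses neither label nor separate it

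*Protocol*

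**What the plan says.** Protocol Table 2-1 gives the Week 4 objective as "To evaluate the efficacy of LOU064 when given without H1-antihistamines in patients with CSU", with three endpoints: change from baseline in UAS7, UAS7≤6 and UAS7=0. Protocol 6.2.1 describes the same four weeks in equally broad terms: "all subjects must start the treatment period (day 1 until Week 4) with LOU064 as a monotherapy without concomitant administration of H1-antihistamines".

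The operative restriction in Protocol 3 is narrower: "Until Week 4 of treatment, no background medication with H1-antihistamines is permitted". The same section adds: "Rescue therapy to treat unbearable symptoms of urticaria on a day-to-day basis with an H1-antihistamine will be allowed throughout the study". Protocol 6.2.3 allows this as needed, with no exception for Weeks 1-4 and no cap on days of use. Table 6-2 bars "Second generation antihistamines other than the defined background medication and rescue medication", so rescue is outside the prohibition.

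Protocol 12.5.1 summarises all three Week 4 endpoints on the Safety Analysis Set (SAF). In SAP 2.6.3 a weekly score becomes missing only when there are too few diary days. Missing binary responses are set to non-response, and continuous scores are summarised as observed. SAP 2.4.2 tabulates rescue by ATC code and preferred term over the treatment period, and lists concomitant medication.

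**The concern.** A reader of the Week 4 tables will take them as the answer to the stated objective. Protocol 4.1.1 shows why the question matters: "the core study assessed efficacy and safety of different doses of LOU064 when given together with H1-antihistamines". The four weeks without background therapy are where this programme can see what LOU064 does without an antihistamine.

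Rescue is the same drug class, and it is taken for the symptoms that UAS7 scores. If some Week 4 responders took it during the scoring week, the tables answer a neighbouring question, and nothing in the visible outputs shows how many subjects that involves. At stake is the interpretation of a descriptive secondary objective. The primary safety objective is unaffected.

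**Working it through.** **1. Objective against permitted treatment, Day 1 to Week 4.**

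| Item | Background H1-antihistamine | Rescue H1-antihistamine |
|---|---|---|
| Objective (Table 2-1) | excluded | excluded, read literally |
| Monotherapy sentence (6.2.1) | excluded | excluded, read literally |
| Conduct rule (Sections 3, 6.2.3; Table 6-2) | barred | allowed as needed |

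**2. What happens to a Week 4 score recorded with rescue.** Under SAP Table 2-1 the Week 4 score uses Days 22-28.
- Score observed, continuous endpoint: used as observed.
- Score observed, binary endpoint: classified by the score alone.
- Fewer than 4 diary days: the score is missing, and the binary endpoint becomes non-response.

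None of these steps refers to rescue. The SAP names a treatment policy strategy in 2.1.1.3, but only for diary data after treatment discontinuation. For rescue the effect is the same, without the label.

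**3. Scale.** The documents give no rescue rate and no expected response rate, so there is no plan figure to reproduce. If a subject who met the criterion with rescue is recounted as a non-responder, the rate falls by 1/n:
- n = 250 (planned enrolment): 1/250 = 0.4 percentage points.
- n = 200 (assumed smaller SAF): 1/200 = 0.5 percentage points.

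More generally, with response rate p and a share q of responders who used an H1-antihistamine on Days 22-28, the planned and supportive rates differ by p × q. Both are assumptions here:

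| p | q = 5% | q = 10% | q = 20% | q = 30% |
|---|---|---|---|---|
| 20% | 1.0 | 2.0 | 4.0 | 6.0 |
| 30% | 1.5 | 3.0 | 6.0 | 9.0 |
| 40% | 2.0 | 4.0 | 8.0 | 12.0 |
| 50% | 2.5 | 5.0 | 10.0 | 15.0 |

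Entries are percentage points. Check: at p = 40% and q = 10%, 250 × 0.40 × 0.10 = 10 subjects, and 10 × 0.4 = 4.0. Each entry is the gap between two ways of counting. It is a ceiling on what rescue contributed, because some of these subjects would have responded without it.

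**4. Can rescue be placed in the window?** Protocol 6.2.1 requires that medications "administered after the subject was enrolled into the study must be recorded on the respective eCRF pages", so the source exists. Incomplete dates are the weak point. Under SAP 5.1.3, an entry with both days missing, in a month after the month treatment started, is imputed from the first to the last day of that month if treatment is still running. That is 28 to 31 days, or 28/7 = 4.0 to 31/7 = 4.4 times the 7-day window. One tablet could then appear to cover all of Days 22-28.

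**The case against.** The strongest reply is that the sponsor always meant without background therapy. Protocol 4.1.1 concerns the choice of background therapy and concludes that a background antihistamine is discretionary. In 6.2.1 the monotherapy sentence stands between two sentences about background medication, and Section 3 treats background and rescue separately. This has real support. It does not remove the point, because the objective and the monotherapy sentence are worded more broadly and no visible text narrows them. If that is the intent, a label settles it.

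Second, the analysis may exist under redaction. Text is hidden in or around the UAS7≤6, UAS7=0 and imputation paragraphs of SAP 2.6, after SAP 2.7.3, in the diary section (Protocol 8.3.1.1) and in Protocol 12.6-12.7. This stands as a limit on the finding; the sponsor may only need to confirm a rule.

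Third, rescue is a reasonable provision for patients, and the study is open-label and single-arm with no hypothesis test. Agreed: nothing here asks for a change in conduct or in the main analysis.

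A reader might go further and infer that the Week 4 results are materially inflated by rescue. The documents do not support that. They give no rescue rate, and rescue is taken when symptoms are bad, so users may seldom be responders. Nor are rescue users protocol violators, since Table 6-2 exempts rescue.

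**Conclusion.** The point holds as a mismatch between the stated question and what the visible analyses describe. The planned Week 4 results are for LOU064 without background H1-antihistamine, rescue permitted. That is a legitimate quantity, but it is not labelled as such, and the visible tables do not show how far it departs from response without any H1-antihistamine.

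The size is unknown. Each rescue-using responder carries at most 0.4 points at n = 250; the totals in the table rest on assumed values of p and q. The conclusion rests on visible text only. It is a cheap improvement to consider and does not invalidate the planned analysis.

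**What to change.** 1. **Label.** In SAP 2.6, keep the planned Week 4 summary as the main one and describe it as *without background H1-antihistamine, rescue permitted*.
2. **Counts.** In SAP 2.4.2, add n (%) of subjects with any H1-antihistamine use on Days 1-28 and on Days 22-28, counted from the efficacy Day 1 of SAP 2.1.1.2 so that they match the diary window. Counting any H1-antihistamine also captures background therapy taken against the protocol.
3. **Supportive analysis.** In SAP 2.6, repeat Week 4 UAS7≤6 and UAS7=0 with any H1-antihistamine user on Days 22-28 counted as a non-responder. This is a conservative lower bound on H1-antihistamine-free response. If rescue cannot worsen scores and earlier use does not carry over into the window, it and the planned summary bracket that response. For mean UAS7 change, the label and counts are enough: a split by rescue use would condition on an event driven by the outcome.
4. **Dates.** Before lock, query incomplete rescue dates that could fall in Days 1-28 instead of relying on SAP 5.1.3.

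The cost is a short SAP amendment, two tables and a few queries, with no new visits or assessments. The drawback is a lower supportive response rate, because one tablet makes a subject a non-responder. For that reason it should remain supportive.

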### 3 Study design

[figure not shown]
This study is an open-label, single arm, multicenter, long-term safety and tolerability extension study for CSU patients rolling-over from CLOU064A2201. It consists of three periods ([Figure 3-1](#)):

- ***Observational period:*** Subjects rolling over from CLOU064A2201 with  $UAS7 < 16$  after the follow-up period at Week 16 will be further followed up without receiving LOU064 for up to 12 weeks. After relapse ( $UAS7 \geq 16$  at least once), the observational period can be terminated immediately at any time during these 12 weeks and subjects may enter the treatment period. Continuation of background therapy with an H1-antihistamine is at the discretion of the investigator; however, background therapy should only be interrupted in subjects with controlled CSU (e.g.  $UAS7 \leq 6$ ). Subjects who have never relapsed within 12 weeks will discontinue the study after the observational period.
- ***Treatment period:*** Subjects will be treated with 100 mg LOU064 bid for 52 weeks. Until Week 4 of treatment, no background medication with H1-antihistamines is permitted. After Week 4, subjects may start a background therapy with H1-antihistamines if deemed necessary by the investigator.
- ***Follow-up period:*** Treatment-free follow-up period following the treatment period. The minimum duration of treatment-free follow-up is 4 weeks for all subjects who stop treatment with LOU064 (either after completing the treatment period or after an early discontinuation of study treatment). Subjects who have a  $UAS7 \leq 6$  at Week 52 of the treatment period will extend their follow-up period until relapse ( $UAS7 \geq 16$ ) for up to a total of 16 weeks.

Rescue therapy to treat unbearable symptoms of urticaria on a day-to-day basis with an H1-antihistamine will be allowed throughout the study. A post-trial access program (which may be another extension study or a managed access program) for subjects who complete this study is under consideration.

**Figure 3-1** Study design

 Only when UAS7<16 at Week 16 of CLOU064A2201: Treatment-free observational period for up to 12 weeks. After relapse (UAS7 $\geq$ 16 at least once), subjects may immediately initiate treatment period. Subjects who have never relapsed within 12 weeks will discontinue the study after the observational period.

[figure not shown]
 The minimum duration of the follow-up period will be 4 weeks for all subjects who stop treatment with LOU064. Subjects who achieve a UAS7 $\leq$ 6 at Week 52 of the treatment period will extend their follow-up period until they relapse (UAS7 $\geq$ 16). Follow-up will stop at Week 68 for all subjects.

 Background therapy is a second generation H1-antihistamine at a locally approved licensed posology given with a stable treatment regimen. Administration/discontinuation of the background H1-antihistamine is at the discretion of the investigator. Background therapy must not be taken from Day 1 until Week 4 of the Treatment period. It may be re-initiated at Week 4 if deemed necessary.

 Rescue therapy is a second generation H1-antihistamine at a locally approved licensed posology that is eliminated primarily via renal excretion (e.g. cetirizine, levocetirizine or bilastine). The rescue H1-antihistamine must differ from the background H1-antihistamine and may only be given to treat unbearable symptoms (itch) of CSU on a day-to-day basis.

Subjects rolling over from CLOU064A2201 will be assigned to one of the periods as follows (Figure 3-2):

- Subjects with a UAS7 $\geq$ 16 at Week 12 or Week 16 will directly enter the treatment period.
- Subjects with a UAS7 < 16 at Week 12 will not rollover into the extension study but enter the follow-up period of the core study CLOU064A2201.
- Subjects with a UAS7<16 at Week 16 (i.e., who have not relapsed during the follow-up period of CLOU064A2201) will be assigned to the observational period.

**Figure 3-2** Patient flow from CLOU064A2201

 Only subjects with a UAS7 ≥ 16 at Week 12 of CLOU064A2201 are eligible to directly rollover into the extension study CLOU064A2201E1 (and directly start with the treatment period). Subjects with a UAS7 < 16 enter the follow-up period of CLOU064A2201.

 After relapse (UAS7 ≥ 16 at least once), the observational period can be terminated immediately and subjects may enter the treatment period. Subjects who have never relapsed within 12 weeks will discontinue the study after the observational period.

## 4 Rationale

### 4.1 Rationale for study design

The major aims of this extension study are to obtain information on the long-term safety and efficacy of a dosing regimen of LOU064 with a high level of BTK occupancy and therefore pharmacological activity, LOU064 100 mg bid for 52 weeks. An open-label study design was chosen to minimize complexity and placebo exposure for CSU patients who have participated in the dose-range finding study CLOU064A2201. A follow-up period of (up to) 16 weeks after the treatment period will further assess safety.

